#### 2.0.4 Outcome of the intervention review

[figure not shown]
A way forward, it appears that individual level of intervention to mitigate mental health issues with re-enforcing of positive emotional and mental health confer robust evidence for the lowincome population. Given the current pandemic climate, internet-based Interventions like CBT and brief mindfulness intervention offer promising psychosocial interventions that strengthen the resiliency at the personal levels to improve the mental health well-being among the B40 group in this country. Even though evidence showed parenting programmes and policy levels are also effective, it was not added in as it more sophisticated evaluation documentation within each household and more interpersonal social contact between the respondents, which is not feasible during the pandemic. To date, there is yet a suitable online manualized psychosocial intervention being tested at the low-income community settings in this country.

## 2.2 Conceptualized Psychosocial Intervention (Health Belief Model )

The current study was conducted based on Medical Research Council (MRC) framework, which was succinctly described in Chapter 1 under **subheading 1.7**. The psychosocial

intervention was developed based on the outcome findings from the cross-sectional study and the qualitative study. Psychosocial interventions for mental health and substance use disorders are interpersonal strategies that are targeted at the level of biological, behavioural, cognitive, emotional, interpersonal, social, or environmental factors in order to improve health functioning and well-being (Butler & Gonzalez, 2015). According to Zoonen et al., timely psychosocial intervention at the pre-clinical stage may avert the development of mental illness (van Zoonen et al., 2014) **Figure 2.2**.

Our psychosocial intervention will be aimed at improving mental health symptoms in order to achieve quality of life. Multiple components of the psychological intervention will be implemented to promote positive mental health by improving the depression and anxiety symptoms of B40 individuals who will be identified through mental health screening. The main components, which entail improving mental health literacy, self-help CBT-based intervention and brief mindful breathing, and providing help-seeking information, will be explained under each domain in the health belief model for promoting behavioural change towards improving health in the methodology.

## Figure 2.2: Intervention at the Pre-clinical stage may avert the mental illness progression. Adaptation from (Zoonan et al. 2014)

Health Belief Model (HBM) has been widely adopted to develop effective interventions that drive changes in health-related behaviours by targeting various aspects of the key constructs in the model (Glanz et al., 2008). The Health Belief Model was developed in the early 1950s by a group of socio-psychologists (Rosenstock & Hochbaum) from the US public health department to understand the reasons for failure of the public to accept the preventive and screening test proposed by the department.

The conceptual model was adapted from Abraham and Sheeran (2005) to explore the perceptions on health preventive behaviours among the B40 towards their current mental health status. HBM permit the understanding of the health belief system that could challenge an asymptomatic individual to take action. This model also guided the situational analysis (mixed methods approach) to identify the baseline risk factors pertaining to individual socio-demographic profiling, psychological characteristics, and recognizing the barriers or fascilitators to help-seeking.

The following section will further conceptualize the psychosocial intervention according to the targeted construct in the Health Belief Model (Figure 2.3).

[figure not shown]

Figure 2.3: Adapted Health Belief Model and Its Relatioship To Research Structure (Abraham & Sheeran, 2015; Rosenstock, 1974)

## 3.0 Methodology

## 3.1 Psychosocial Intervention Module Development

Psychosocial Intervention Module development is to answer the **Objective 4** of this study, is a follow up of the mixed methods study before under the phase 1 development phase of the MRC framework. The module development intends to consolidate the evidence from the literature review and the findings from the situational analysis (mixed methods study) to form a standardized module guided psychosocial intervention through psychoeducation for the targeted low-income population.

As this is a health promotion psychosocial intervention based on health belief model (HBM), two main themes, barriers and facilitators derived from data integration will be mapped to form the domains for the module development.

It will be followed by setting of the objectives for each domain by using SMART approach .

3.1.1 Mapping the Components for the development of "ReSHape" online Modules Mixed methods study in this research has proven, mental health issues are high and affecting the quality of life among the B40 community at the Petaling district. This warrant further psychosocial intervention.

The intervention will be developed to improve the mental health status and quality of life among the B40 community by improving their skill in recognising common mental health issues, selfhelp and help-seeking. This will be based on factors that emerged from the final data triangulation between quantitative and qualitative study, which comprised mental health literacy, resilience (self-reliance, religiosity and social support) and help-seeking. Poverty attribution is a factor to explain the perceptions of the poor with good coping factors like selfreliance helps them to thrive amid adversity.

The three components identified were mental health literacy and help-seeking, while the facilitator was self-reliant. The psychosocial intervention modules were formulated based on

the Health Belief Model (HBM) concept to drive a person to adopt healthy behaviours, and objectives of the main components were developed based on the SMART approach.

- 1. **Specific**:- Objectives specific for each module.
- 2. **Measurable:-** The comprehension of each module will be measured by pre and postassessment and evaluation by using specific research tools (Primary and Secondary outcomes).
- 3. Achievable: A video tutorial (10 to 15 minutes) was sent to the participants the first week, followed by an assessment on the second week.
- 4. **Realistic:-** ReSHape Modules will be able to implemented and tested in the community
- 5. **Timely:** these modules are expected to successfully delivered at the community settings

In the HBM model, improving mental health literacy helps to recognise the severity of the disease condition. Next, depression and anxiety symptoms can be alleviated by applying **self-help** approach through Cognitive Behavioral therapy **(CBT)** and mindful breathing exercise. Finally, with the mental health information and psychoeducation, the respondents will be prompt to **seek help**. **Specific:-** The specific objectives of each module guided the design of the activities.

#### 3.1.1.1 Components that promote the Behavioral Change

#### a) Recognise the Need for Change

The first **Module 1 Recognise: Knowing Your Mental Health** is based on the limited mental health literacy, the misconception of mental health and lack of awareness of the available treatment among the B40 respondents. The aims are to provide essential information on the definition of mental health, contributory factors, symptoms of depression and anxiety, treatment options, the myth of mental health and the importance of mental health screening. Improving mental health literacy improves the public's stigmatising perceptions on mental health issues and encourages an individual to seek help. Mental health screening using PHQ-9 and GAD-7 helps an individual aware of the severity and susceptibility of their mental health issues. As described in the HBM, when individuals feel the threat of the disease, they will seek help.

#### b)Self Help

Depression and anxiety were elevated among B40, and the qualitative study showed most of the participants prefer self-help as one of their initial options to resolve the underlying mental health issues. This **Module 2 Self-help** comprises three submodules based on CBT concepts, and one module focuses on mindfulness breathing exercises. These are evidence-based psychosocial interventions to reduce symptoms of depression and anxiety while improving their positive coping

Based on the Beck (1979) Cognitive model, an individual emotion and behaviour are influenced by the perceptions environment. By applying the cognitive triad formulation suggested by , which comprises core beliefs, dysfunctional assumptions, and negative automatic thoughts, it assists in reconstructing the maladaptive cognition in mental health issues. Therefore The first three sub-module in ReSHape module 2 use Cognitive behavioural therapy (CBT) approaches to reduce depression and anxiety symptoms through three key strategies **a**) **Problem-oriented goal setting, b**) **behaviour activation and c**) **Recognising and overcoming negative thoughts.** The ultimate aims of this module are to provide the B40 skills to understand their current ways of thinking, behaving and equip them with the tools to change their maladaptive cognitive and behavioural pattern(Fenn & Byrne, 2013). Reducing negative thoughts increases the motivation in individual who has high symptoms of depression or anxiety(Beck, 1979).

The first **sub-module 2A is problem-oriented -goal setting**. Respondents were guided on recognising their strengths, identifying problems, and setting goals to reduce their issues in life that lead to mental strain. With that, the respondents were required to suggest three issues in life i.e, and not enough rest causes stress leads to unhealthy eating, leads to overweight; strategies to resolve their issues for the next three months is sleep early.

The subsequent **sub-module module 2B behaviour activation** provide respondents with skills to activate what they have planned. They are required to set up a digital calendar reminder and required to keep a record of what they have done and what not in a self-evaluation weekly form (Appendix G). This prompt an individual to take action on the subsequent week according to the planned activities.

At time, respondents may face the challenge of negative thoughts due to their daily stressful life, and the **sub-module 2C negative thoughts** help them identify the negative thoughts and overcome them guided by another self-evaluation form (Appendix H).

The low-income group is a stressful community with their hectic routine, the final module, Mindfulness breathing exercise, provides stress reduction techniques that bring them to focus. According to evidence, a mindful breathing session that lasts for 15 to 20 minutes, three to four times a week, reduce depression and anxiety symptoms.

Reducing negative thoughts stemming from underlying mental issues improves the respondents' motivation to adopt health promotion for their mental well-being. Harnessing the strength of the respondents mediate the respondent's motivation to overcome negative thought that equates as a barrier that is emphasized in the HBM.

#### c)Help-seeking

The quantitative study results showed equivocal findings for Mental Health help-seeking attitudes and were challenged by the reduced trust to see the professional. Therefore, this module seeks to create awareness of the dangerous sign of severe mental illness and when they should seek -help. Again, this is to raise the respondents' awareness on how severe their condition is that warrant them to seek the needed treatment.

In this module, respondents were provided with information on the credible organization they can seek for help and surf safely online.

#### 3.1.2 Mode of delivery

An online / internet-based mode of delivery will be opted for ReSHape psychosocial intervention for its feasibility during the movement restriction amid the COVID-19 pandemic. This intervention research will be developed in REDCap to facilitate the delivery of the modules and data collection. REDCap, University Malaya is a secure web platform for building and managing for online databases and surveys. REDCap's streamlined process for rapidly creating and designing projects offers a vast array of tools that can be tailored to virtually any data collection strategy (Harris et al., 2009)

#### 3.1.3 Development of the activities and content

The specific objectives of the modules were translated into the Malay language by the nativespeaking research assistant for the current study precede the drafting of the module's content. The content was worded in simple Malay language with minimal technical terms suitable for the literacy level of the B40 community, which is on par with 6th grade or standard six reading level and below. The investigators also sourced information from the Infosihat from the Ministry of Health, Malaysia, Health Education of England (HEE) and National Institutes of Health, USA. The contents of the modules were presented in PowerPoint and reviewed by an academician and a senior counsellor before it was converted to video format. Attractive graphics will be added to each narration to enhance the understanding of the contents. A situational narrative or a case study will be created in modules 2A and 2B to portray the meaning of negative thought and overcome it. Each video was kept between 5-10 minutes. The videos will be uploaded to youtube first before they will be linked to ReDCap. The six modules will be delivered online through RedCAP over 12 weeks duration, whereby each respondent will be given one module link (started from the first module in the first week and ended with the last module at twelve-week) every fortnight through an email account or Whatsapp. Each respondent will be given ample time to clarify their doubts with the investigators and answer all the assignment before moving on to the subsequent module. The estimated duration for each respondent was 3-4 hours **Table 3.1**. Each respondent will be given a unique ID in the ReDcap, and upon completion of the modules, the link will be locked to avoid sharing of the link with other respondents.

Table 3.1 Relevant modules assignments, activities and duration for completing
each module

	MODUL	Activities	Estimated Duration	
		Video ,	10 minit	
Modul 1 :K	enali Minda Anda	Menjalankan Saringan Minda Sihat , Quiz berkenaan dengan Modul	20 minit	
Modul 2:	24. Dava Katabanan	Video	10minit	
Membantu Diri	2A: Daya Ketahanan Minda dan Menentukan Matlamat	Quiz, Borang Menentukan Matlamat	20 minit	
		Video	10-minit	
	2B: Mengambil Tindakan	Quiz dan Borang Pemantauan Mingguan	45 -minutes	
		Video	10 minit	
	2C: Mengatasi Fikiran Negatif	Quiz dan Borang Pemantauan Pemikiran Negatif	35 minit	
	2D: Kesedaran	Video +	10 minit	
	Pernafasan (Mindfulness)	Quiz dan Soal selidik Minfulness Awareness	35 minit	
Modul 3 · Me	endapatkan Bantuan	Quiz	15 minit	
		Video	15 minit	
	Total			

[figure not shown]
# 3.2 Phase 2 Intervention : Feasibility and Evaluation Community-Based Intervention Study.

Phase 2 of this research involved the piloting and evaluation phase in the MRC framework, whereby the feasibility and effectiveness of ReSHape modules will be assessed through a community-based experimental study that will be incorporated into a logic evaluation model. Feasibility studies are commonly used to determine whether an intervention can be shaped to be relevant and sustainable for further testing in a bigger-scale study among the targeted population (Bowen et al., 2009). ReSHape modules will be tested in the community or in real-world settings, as mental health is not merely affected by individual behaviour but also closely related to socio-environmental factors. Therefore when intervention is done at the community level, it gives an interpersonal effect to drive the changes (Butler and Gonzalez 2015). And the areas of focus in the current feasibility study are the acceptability and the practicality of ReSHape modules to be used among the B40 community in the "real world" setting, guided by a process evaluation in the logic model to ensure fidelity. These are helpful information to troubleshoot any technical issues with the intervention module before implementing the community.

#### 3.2.1 Study design

An online controlled pre-and post-quasi-experimental study will be piloted with an evaluation in a logic model to assess the feasibility and effectiveness of the ReSHape modules. Quasiexperimental is a cost-effective study design with good practicality for "real world" communitybased intervention. ReSHape modules will be delivered through RedCAp online platform, as face to face intervention was impossible during the COVID-19 pandemic due to the movement control restriction at Petaling District. This study had been registered under ISRCTN25880061 (ISRCTN, 2021). The study will be conducted in Feb 2021 and ended in August 2021. The study will be reduced from 6 months to 3 months due to the shortage of funding.

The online quasi-controlled experimental study will be evaluated through process evaluation and outcome evaluation. Data collection will be conducted at pre-test T0 and post-test T1, after three months using validated tools (**Figure 3.1**). A post-test analysis at the post-intervention period will be conducted to look for differences between the intervention arm and the control arm. The feedback on the acceptability of the module's activities will be collected using a module evaluation form (kindly email the principal investigator to view the form).

#### 3.2.2 Study Site and Target Population

3 months

Eligible respondents from the low-socioeconomic households will be recruited from the four sub-districts of Petaling Districts, namely Sungai Buloh, Petaling Jaya, Damansara and Bukit Raja (refer to Stuty site 3.3.1), through a social media campaign, whereby video of recruitment and electronic posters will be emailed to all the heads of the community. Preliminary screening for potential respondents will be done. Baseline assessment in Google form will be sent to the community leaders at the four sub-districts and filled by the low socioeconomic households.

Two medical officers trained in mental healthcare will be kept in standby and screened through the respondents' baseline assessment based on PHQ-9, GAD-7 and history of current mental illness. Eligible respondents will be recruited, and the consent form will be electronically signed in the REDCap database before data collection. Since this is a controlled quasi-experimental study, no randomization will be done, respondents from Lembah Subang 1 were assigned to the intervention group, while respondents from Lembah Subang 2 will be put under the control group.

A letter of invitation, respondent's info sheets, and consent forms will be sent through RedCaps. Consent was obtained before the commencement of the study using the consent form attached in the ISRCTN registry.

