## 1.6.2 Phase 2: Feasibility Study and Evaluation

## **Controlled-Quasi Experimental study**

## **Specific Objectives 5**

To evaluate the effectiveness of the psychosocial intervention through a) outcomes evaluation and b)process evaluation

- a) Outcomes evaluation is done through controlled-quasi-experimental study with pre-test and post-test to assess the change in primary outcomes (depression anxiety and quality of life) and secondary outcomes (BMI, poverty attribution (PA-21), self-stigma (SSOSH), mental help-seeking attitude (MHSAS), strength of religiosity (SCSRF-5) health literacy(HL-6) and psychology resilience(RS-14).
- b) Process evaluation: evaluation form to assess the agreement, acceptance and feedback from the low-income respondents.

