### 3.2.2.1 Eligibility Criteria

### Inclusion criteria

The respondent is 18 years old and above. Mild to moderate score on PHQ-9 ( ≥5 < 10)

 and GAD-7 (≥5 <8) living in the three subdivisions of Petaling District.

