# Table 3.6: Content Validity Index (CVI) and feedbacks from the panel experts for Reliability Questionnaires

In order to assess the reliability of the module, a feasibility study needs to be conducted at Projek Perumahan Rakyat (PPR) Lembah Subang One. Through purposive sampling, forty-five lowincome respondents were recruited to test for the reliability of the intervention modules.

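### Each arm is one named site, so the between-arm contrast cannot by itself establish effectiveness, and the recruitment, inclusion and allocation texts name different areas.

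*Protocol*

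**What the plan says.** On allocation, Protocol 3.2.2 states that "no randomization will be done" and then that "respondents from Lembah Subang 1 were assigned to the intervention group, while respondents from Lembah Subang 2 will be put under the control group". No second site in either arm is mentioned.

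On who may enter, the same section says respondents are "recruited from the four sub-districts of Petaling Districts, namely Sungai Buloh, Petaling Jaya, Damansara and Bukit Raja". The inclusion criterion in 3.2.2.1 instead asks for people "living in the three subdivisions of Petaling District". Neither Lembah Subang site is among the four named sub-districts.

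On aim, objective 5 (1.5.3 and 1.6.2) is "To evaluate the effectiveness of the psychosocial intervention through a) outcomes evaluation and b)process evaluation". Section 3.2.1 repeats feasibility and effectiveness as the purpose, and 1.6.2 sets between-arm hypotheses for the primary and secondary outcomes.

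On analysis, 3.2.7.2 defines the effect as the intervention arm's pre-post change minus the control arm's. It models outcomes by MMRM, or logistic GLMM for EQ-5D, and interprets results at the 0.05 level. Baseline tests are the stated check on comparability.

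Section 3.2.6.2 adds that "a feasibility study needs to be conducted at Projek Perumahan Rakyat (PPR) Lembah Subang One" and that "Through purposive sampling, forty-five lowincome respondents were recruited to test for the reliability of the intervention modules". It does not say how these 45 relate to the 50 per arm in 3.2.5.

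**The concern.** With one site per arm, anything that happens at one site and not the other between T0 and T1 moves the arm contrast exactly as an intervention effect would. The protocol gives reason to expect such influences: section 3.2 says mental health is closely tied to socio-environmental factors, and the study runs during pandemic restrictions. A significant result could be reported as effectiveness when the data cannot tell the two explanations apart, and an individual-level p-value carries no allowance for site.

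The second problem is operational. Read literally, a person can be recruited and eligible under the area wording yet fall under no allocation rule.

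**Working it through.** **1. What the contrast removes.** Write the mean change in an arm as change common to both sites, plus change specific to that site, plus the intervention effect (intervention arm only).

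- Intervention minus control = intervention effect + (site-specific change at Lembah Subang 1 − site-specific change at Lembah Subang 2).
- Stable site differences cancel within each arm's pre-post difference. Common change cancels between arms. The bracket stays.
- A site term in the model would be collinear with arm. Baseline tests look at T0 only. Raising the number of residents narrows individual error but leaves the bracket unchanged.

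**2. The planned number.** Section 3.2.5 gives 50 per arm after a 20% reserve, from d = 0.42, 0.05 and 80% power. I could not reproduce it from those inputs: a two-sided independent-groups t-test needs 90 per arm (113 after dividing by 0.8), and a two-sided paired test needs 47 (59 after inflation). The test, sidedness and pre-post correlation are not stated, so this remains a separate question. It does not affect step 1. I use 50 per site as the upper case and 50 × 0.8 = 40 as the lower.

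**3. Illustration of size.** The intra-site correlation (ICC) of the change score is **assumed**; the documents give none.

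- Design effect: DEFF = 1 + (m − 1) × ICC, with m analysed per site.
- True two-sided error of a nominal 5% test that ignores site: 2 × [1 − Φ(1.96/√DEFF)].
- Example, m = 50, ICC = 0.02: DEFF = 1 + 49 × 0.02 = 1.98; 1.96/√1.98 = 1.393; error = 16.4%.

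| | ICC 0.005 | ICC 0.01 | ICC 0.02 | ICC 0.05 |
|---|---|---|---|---|
| m = 50, DEFF | 1.245 | 1.49 | 1.98 | 3.45 |
| m = 50, true error | 7.9% | 10.8% | 16.4% | 29.1% |
| m = 40, DEFF | 1.195 | 1.39 | 1.78 | 2.95 |
| m = 40, true error | 7.3% | 9.6% | 14.2% | 25.4% |

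The same point without an ICC: suppose the intervention does nothing but the sites drift apart by 0.2 SD (assumed). With 50 per arm the standard error is √(2/50) = 0.20 SD, and the test is significant 17.0% of the time. With 40 per arm it is 14.5%.

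**4. The areas side by side.**

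| Text | Areas |
|---|---|
| Recruitment, 3.2.2 | four sub-districts, named |
| Inclusion, 3.2.2.1 | three subdivisions, not named |
| Allocation, 3.2.2 | two sites, neither among the four names |

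This mismatch needs no assumption.

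**The case against.** The design is openly declared as non-randomised. Section 3.2 puts the focus on acceptability and practicality ahead of a larger study, and 3.7.8 commits to the TREND checklist. One site per arm is a familiar limitation of such a pilot, and a controlled pre-post comparison is much better than none. That stands, and it is why the remedy is wording. It does not cover objective 5, 3.2.1 and the hypotheses, which go beyond feasibility.

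The size rests on an assumed correlation. Delivery is individual and online, and movement restrictions across the district were probably shared by both sites, so site-specific change may be small. That also stands: the error rates are illustrative and should not be cited as properties of this trial.

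The wider areas may be only the advertising catchment, with both sites inside a named sub-district. Section 3.2.2 refers to a study-site section, 3.3.1, that is not in the document at hand. This is possible, but the current text does not say so.

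A reader might go further in three ways that the documents do not support:

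- **Both arms are housing projects.** Only Lembah Subang One is called one (3.2.6.2); for the second site it is an inference from the name.
- **The 45 are a separate, already exposed group who must be excluded.** Section 3.2.6.2 places reliability testing in a feasibility study at the intervention site, and Phase 2 is that feasibility study. The likelier reading is that they are the intervention arm.
- **The trial must be redesigned.** Two sites per arm would leave 4 − 2 = 2 site-level degrees of freedom (critical t 4.30). Randomising within site changes the declared design and risks contamination between neighbours.

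**Conclusion.** The point holds as a limit on inference and as a contradiction in the text. Arm and site are fully confounded under the allocation rule as written, so the tests cannot by themselves establish effectiveness. This follows from the structure and needs no assumed value. It does not make the estimate worthless, and it leaves the acceptability and practicality aims untouched.

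The true error of about 7% to 29% depends on an assumed ICC of 0.005 to 0.05 and 40 to 50 analysed per site. It shows that a small site correlation is enough to matter, not what the correlation is. The conflict between four, three and two areas stands on the text alone.

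**What to change.** 1. Make the recruitment paragraph, the inclusion criterion and the allocation sentence name the same sites. If the wider areas are only where the study is advertised, say so. State whether the 45 respondents in 3.2.6.2 are the intervention arm; if they are a separate group, say how their prior exposure to the modules is handled.
2. Reword objective 5, section 3.2.1 and the 1.6.2 hypotheses so that the two-site contrast is a preliminary estimate, confounded with site, that does not establish effectiveness. Add to 3.2.7.2 that individual-level p-values and intervals exclude site-level variation.

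Both are wording changes with no effect on recruitment numbers, data collection or delivery. What the sponsor gives up is an effectiveness claim that the design cannot carry. More sites per arm, or randomisation within site, are options for the later, larger study and not requirements here; their costs are few site-level degrees of freedom in the first case and contamination between neighbours in the second.
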